3.3.4 Implant loss/removal and Implant magnet loss/removal

- Has the patient lost/removed the implant?
 - Yes
 - No
- Date of loss/removal of implant
- Has the patient lost/removed the implant magnet?
 - Yes
 - No
- Date of first loss/removal of implant magnet

Protocol:

Post-market clinical follow-up of a magnetic bone conduction implant

Protocol No:

CBAS5477

Version:

1.0

Page 12 of
18

4 STATISTICAL METHODOLOGY

4.1 General Methodology

Since all included subjects will have measurements of the primary and important secondary efficacy variables for unaided hearing, with the sound processor on a Softband and with the Baha Attract System, all statistical analyses will be paired. All statistical analyses will be non-parametric. In order to choose the most powerful test, the Fisher's non-parametric permutation test for paired observations will be used for all paired analyses of continuous variables. The permutation tests use the measured values and not only the ranks in the calculations. For paired analysis of dichotomous and ordered categorical variables the Sign test will be used.

The analyses will be performed in the following priority:

1. Baha Attract System vs. Unaided
2. Baha Attract System vs. the sound processor on a Baha Softband

In addition to the change variables the distribution of all efficacy variables will be presented by visit, where applicable.

The main efficacy analysis will be performed on the ITT population and complementary efficacy analyses will be performed on the PP population. The main analysis will be performed after the 6 month visit. A complementary analysis will be performed 18 months after the main analysis (24-month visit). All significance tests will be two-sided and performed at the 5% significance level.

Imputation of missing values will be performed for all efficacy variables. No imputation of baseline values will be made. Imputations will be made according to the following rules:

1. If a value is missing at the end of a patient last observation will be carried forward
2. If a missing value is occurring between two time points with values, an interpolation will be made for continuous variables and for categorical variables the value from the previous visit will be carried forward.

The distribution of continuous variables as well as change in continuous variables will be given as n, mean, SD, SEM, Median, Min and Max and the distribution of dichotomous and categorical variables will be given as number and percentages.

Adverse Events, Device deficiencies, Surgical variables, Demographics Baseline, Questions, Magnetic force and Magnet strength variables will only be analysed descriptively.

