1.1.2 Secondary objectives

- To compare the hearing performance with the Baha Attract System and the hearing performance with the same sound processor on a Baha Softband.
- To compare health status, health-related quality of life and utility scores before and after use of the Baha Attract System.
- To compare the self-reported assessment of hearing aid outcome before and after use of the Baha Attract System.
- To collect surgical information.
- To investigate if the Sound Processor Magnet strength and magnetic force required for retention changes over time.
- To collect information regarding pain, discomfort, numbness and soft tissue status.
- To monitor implant survival.
- To collect Adverse Events and device deficiencies.

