3.2.2 Secondary Efficacy Variables

- Thresholds audiometry: 250, 500, 1000, 2000, 3000, 4000, and 6000 Hz at visit 1, w 4, m 6, m 12 and m 24.
- Adaptive speech recognition in noise (50% performance) at visit 1, w 4, m 6, m 12 and m 24.

Protocol:

Post-market clinical follow-up of a magnetic bone conduction implant

Protocol No:

CBAS5477

Version:

1.0

Page 10 of
18

- Speech perception in quiet (50dB, 65dB and 80dB SPL) at visit 1, w 4, m 6, m 12 and m 24.
- BC Direct thresholds at visit 1 and w 4
- Generic quality of life scale: Health Utility Index (HUI):
 - Health related quality of life score for overall health
 - Vision score
 - Hearing score
 - Speech score
 - Ambulation/mobility score
 - Dexterity score
 - Self-care score
 - Emotion score
 - Cognition score
- Abbreviated Profile of Hearing Aid Benefit (APHAB):
 - Ease of Communication
 - Reverberation
 - Background Noise
 - Aversiveness
 - Global score
- The Speech, Spatial and Qualities of Hearing Scale (SSQ)

Surgical variables

- Soft tissue thickness (mm)
- Surgery time (time of first incision to time of last suture), (min)
- Soft tissue thinning performed
 - Yes
 - No
- Bone polishing/removal performed
 - Yes
 - No
- ISQ Low
- ISQ High
- BI300 length
 - 3 mm
 - 4 mm

Questions regarding Sound processor magnet by visit and changes over time (w 4, w 6, w 12, m 6, m 12 and m24)

- Choice of SP Magnet (SPM1 (weakest), SPM2, SPM3, SPM4, SPM5, SPM6 (strongest))
- Mean Magnetic retention force (mean of three values). If there is large variations within the three measurements median of the three values will be used instead.

Questions about usage will be collected for w 6, w 12, m 6, m 12 and m24:

- Daily use of SP (hours/day)
- Number of times SP fell off during last week
- Number of times SP fell off during last week per Daily use (times/hours/day)
- Number of Soft pad changes per week (calculated from changes last week and changes last month)
- Number of Soft pad changes per Daily use (changes/hours/day)

Protocol:

Post-market clinical follow-up of a magnetic bone conduction implant

Protocol No:

CBAS5477

Version:

1.0

Page 11 of
18

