4.10.2 Secondary Efficacy Analyses

Comparison regarding change from unaided hearing to Baha Attract System will be done according to the general methodology with Fisher's non-parametric permutation test for paired observations for the following variables:

- Threshold audiometry: PTA4 (Mean of 500, 1000, 2000 and 4000 Hz) at 4 weeks, 12 and 24 months
- Threshold audiometry: 250, 500, 1000, 2000, 3000, 4000 and 6000 Hz at 4 weeks, 6, 12 and 24 months
- Adaptive speech recognition in noise (50% performance) at 4 weeks, 6, 12 and 24 months
- Speech in quiet (50dB, 65dB and 80dB) at 4 weeks, 6, 12 and 24 months
- HUI3 at 6 and 24 months
- APHAB at 6 and 24 months
- SSQ at 6 and 24 months

Comparison of the Baha Attract System with the same sound processor worn on a Softband will be done according to the general methodology with Fisher's non-parametric permutation test for paired observations for the following variables:

- Threshold audiometry: PTA4 (Mean of 500, 1000, 2000 and 4000 Hz) at 4 weeks, 6, 12 and 24 months
- Threshold Audiometry: 250, 500, 1000, 2000, 3000, 4000 and 6000 Hz at 4 weeks, 6, 12 and 24 months
- Adaptive speech recognition in noise (50% performance) at 4 weeks, 6, 12 and 24 months
- Speech in quiet (50dB, 65dB and 80dB SPL) at 4 weeks, 6, 12 and 24 months

Magnetic force studied both total and by SP magnet. Changes in SP magnet strength will also be presented graphically in a flow graph.

All secondary efficacy analyses will be performed for both the ITT population and PP population. PTA4 will also be analyzed for the PP population in the same fashion as in the primary analysis.

Analyses of Threshold Audiometry, Adaptive speech recognition in noise and Speech in quiet, BC Direct, HUI, APHAB and The Speech, SSQ will be a made totally and also by SSD and Conductive/Mixed patients. This will be made only for the ITT populations.

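### SAP 4.1 imputes SP Magnet choice and its retention force by different rules, so a few interpolated forces that mix two magnets are tabulated under the earlier one (minor, descriptive outputs only)

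*SAP*

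**What the plan says.** SAP 4.1 General Methodology sets the scope: "Imputation of missing values will be performed for all efficacy variables", with baseline values excepted. Rule 1 covers values missing at the end of follow-up: "If a value is missing at the end of a patient last observation will be carried forward". Rule 2 covers a gap between two observed visits: "an interpolation will be made for continuous variables and for categorical variables the value from the previous visit will be carried forward".

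SAP 3.2.2 Secondary Efficacy Variables lists the choice of SP Magnet (six ordered strengths) and the mean retention force (mean of three readings), both at weeks 4, 6 and 12 and months 6, 12 and 24. Protocol 5.2.2 also lists both as secondary efficacy variables. No text exempts them from imputation or links how the two are imputed.

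SAP 4.10.2 plans the stratified summary: "Magnetic force studied both total and by SP magnet". The outputs are the sound processor magnet tables numbered 14.2.8.1 and 14.2.8.2 (numbers that the list also gives to two SSD speech tables), Figure 14.2.4 (force, total and by magnet strength) and Figure 14.2.3 (flow graph of magnet strength). They serve a stated secondary objective in SAP 1.1.2: "To investigate if the Sound Processor Magnet strength and magnetic force required for retention changes over time". SAP 4.1 restricts magnet force and strength to descriptive analysis.

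**The concern.** Under Protocol 6.20, force is measured with the SP Magnet in place over the Implant Magnet, so a force value has meaning only together with the magnet that produced it. Rule 2 separates the two. When the magnet differs before and after a missed visit, the record keeps the earlier magnet but receives a force drawn partly from the later one. That force was never measured on the magnet under which it is reported.

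Rule 1 raises a second issue. A subject who leaves keeps the last magnet and the last force at every later visit, so change after departure is zero by construction. The objective is to see whether these quantities change, and subjects without data are counted as evidence that they do not.

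At stake is the accuracy of the by-magnet force summaries, the flow graph and the change summaries.

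**Working it through.** **Inputs from the documents.** 52 subjects and 10% drop-out (SAP 1.4.3; 46/0.9 = 51.1, which rounds up to the stated 52). Six visits with magnet and force data, of which four (week 6, week 12, month 6, month 12) can be gaps between observed visits. Visits 8 and 9 are not part of the six-month analysis (SAP 1.2.1, footnote to the flowchart). Magnet decisions are made at Visits 4–9 and at extra visits (Protocol 6.19).

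**Inputs assumed, because the documents give none.** Probability m = 5–10% that an intermediate visit is missed; probability p = 10–20% of a magnet change per interval; illustrative forces in newtons.

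**1. How far one interpolated force is off.** With linear interpolation in time, the weight on the next visit's force is w = (t_missed − t_previous)/(t_next − t_previous). In days:

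- week 6: (42 − 28)/(84 − 28) = 0.25
- week 12: (84 − 42)/(182.6 − 42) = 0.30
- month 6: (182.6 − 84)/(365.25 − 84) = 0.35
- month 12: (365.25 − 182.6)/(730.5 − 182.6) = 0.33

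The SAP does not say whether interpolation is by time or by visit order; by visit order the weight is 0.50.

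Take a missed week 12, with 1.0 N on the earlier magnet and 1.5 N on the later one. The imputed force is 1.0 + 0.30 × 0.5 = 1.15 N by time, or 1.25 N by visit order, and it is listed under the earlier magnet. In an assumed row of eight subjects, one such value moves the row mean by 0.30 × 0.5/8 = 0.02 N to 0.50 × 0.5/8 = 0.03 N.

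**2. How many such pairs to expect.** If magnets change only at attended visits, a missed visit gives a mixed pair when the magnet is changed at the next attended visit. Ignoring drop-out and gaps of more than one visit, the expected number is 52 × 4 × m × p:

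- low: 52 × 4 × 0.05 × 0.10 = 1.04
- high: 52 × 4 × 0.10 × 0.20 = 4.16

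Simulation of 52 subjects with 10% drop-out gives 1.0 to 3.7.

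If magnets could also change at the time of the missed visit, for example at an extra visit, p is replaced by about 1 − (1 − p)², that is 0.19 to 0.36. The result is 52 × 4 × 0.05 × 0.19 = 1.98 to 52 × 4 × 0.10 × 0.36 = 7.49 (simulation 1.8 to 6.8).

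**3. Which analysis they fall in.** In the six-month analysis Month 6 is the last visit. A missed Month 6 therefore falls under rule 1, and magnet and force are carried forward together from week 12 as a matched pair. Only weeks 6 and 12 can be interpolated: 52 × 2 × 0.05 × 0.10 = 0.52 to 52 × 2 × 0.10 × 0.20 = 2.08 (simulation 0.4 to 1.8). The other half, at months 6 and 12, arises only in the 24-month analysis. A missed Month 6 force can therefore take one value in the first analysis and another in the second.

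**4. LOCF and change from Month 6 to Month 24.** If all who leave have no data after Month 6, the reported share changing magnet is the true share × (1 − d). At d = 10%, a true 20% is shown as 0.20 × 0.90 = 18%. Some leave later and keep part of their change. Simulation at 10% drop-out and 5% missed visits, with changes allowed at any visit, gives 18.8% reported as 17.6% (1.2 points) and 33.3% reported as 30.8% (2.5 points). On 52 subjects, 2.5 points is 0.025 × 52 = 1.3 subjects.

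**The case against.** The strongest reply is that little depends on this. The outputs are descriptive; no test, significance level or sample size uses them. At the planned drop-out the LOCF effect is about one subject in 52. SAP 4.2 tabulates withdrawals and their reasons, so the missing subjects are visible elsewhere. All of this stands and is why the point is minor.

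A reader might infer that the imputed magnet and the imputed force are both wrong. Protocol 6.19 does not support that: magnets are changed at scheduled or extra visits, so a subject who misses a visit and has no extra visit is still wearing the earlier magnet. The fault is then in the force alone. The label can be wrong only if the magnet was changed at an extra visit within the gap, and the documents give no rate for that.

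A reader might also infer that the main six-month result at Month 6 is affected. It is not, because the pair is carried forward intact there. Nor do the documents support a claim that the by-magnet table will show a false drift in force: they contain no force values, and one mixed value moves a small row by only a few hundredths of a newton under the forces assumed above.

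Finally, the SAP does not say outright that these tables and figures use imputed values, and the heading of SAP 3.2.2 also covers single-time surgical variables to which neither rule can apply. The intended scope may be narrower than the wording. As written, though, the rule covers all efficacy variables. The restriction to descriptive analysis removes testing, not imputation.

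**Conclusion.** The point holds on the literal wording of SAP 4.1 and is minor. A missed intermediate visit with different magnets on either side produces a force that mixes two magnets, reported under the earlier one. This happens about 1–4 times per trial if magnets change only at attended visits, and more often if they change at extra visits. About 0.5–2 of these fall within the six-month analysis; the rest arise only in the 24-month analysis. If the same magnet is worn on both sides of the gap, there is no conflict.

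LOCF understates the share of subjects changing magnet between Month 6 and Month 24 by about 1–3 percentage points at 10% drop-out. Change observed before departure is kept.

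The counts rest on assumed missed-visit and change rates, and the newton figures are illustrations only. The primary analysis and the tested secondary comparisons are untouched. No defect was shown for the usage questions (daily use, retention episodes, Soft pad changes), so the conclusion does not extend to them.

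**What to change.** In SAP 4.1, exempt SP Magnet choice and retention force from imputation and state that both are summarised on observed values, with n given per visit. In the sound processor magnet tables (14.2.8.1 and 14.2.8.2) and Figure 14.2.4, use only force readings paired with the magnet measured at that visit. In Figure 14.2.3, show missing or withdrawn subjects as a separate stream instead of carrying their last magnet forward.

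A narrower clause, that force is not interpolated across a change of magnet, would cure the mixed pairs but not the LOCF effect on the change-over-time objective.

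The cost is SAP wording and a smaller n at later visits in descriptive tables. Protocol 8.4 contains no imputation rule, so the protocol needs no amendment.

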4.2 Patient Disposition and Data Sets Analyzed

The number of subjects included in each of the ITT, PP and Safety populations will be summarized. Subjects who completed the study and subjects who withdrew from study prematurely will also be presented with a breakdown of the reasons for withdrawal by treatment group for the ITT, PP and safety populations.

Reasons:

- Eligibility failed
- Intra-operative failure

Protocol:

Post-market clinical follow-up of a magnetic bone conduction implant

Protocol No:

CBAS5477

Version:

1.0

Page 13 of
18

- Subject non-compliance
- Major Protocol Deviation affecting the primary endpoint
- Lost to Follow-up
- Discretion of the investigator
- Subject withdrew Consent
- Intolerable Adverse Event
- Death
- Other

4.3 Protocol Deviations

Major protocol deviations are those that are considered to have an effect on the analysis. The number of patients with major protocol deviations will be summarized per treatment group. A list of protocol deviations will be produced.

4.4 Demographics and Baseline Characteristics

Demographics and baseline characteristics will be descriptively summarized for the ITT and PP populations.

4.5 Pre operation variables

Pre operation variables will be summarized for the ITT and PP populations and analyzed according to the methods described in section "General Methodology" above.

4.6 Audiogram

Audiogram at visit 1 will be presented for the ITT and PP populations by Air condition/Bone conduction, Baha side/Non Baha side, Unmasked/Masked for 250, 500, 750, 1000, 1500, 2000, 3000, 4000, 6000 and 8000 Hz by SSD and Conductive/Mixed patients. In addition to the tables, figures will be produced for the audiogram data.

4.7 Medical and Surgical History

Medical and surgical history, one at a time, will be summarized by system organ class (SOC) and preferred term (PT) for each treatment group for ITT population.

4.8 Prior and Concomitant Medications

Prior and concomitant medication will be summarized by higher level anatomical therapeutic classification (ATC) group and generic term for each treatment group for ITT population.

4.9 Concomitant Treatments/Procedures

Concomitant treatments/procedures will be listed for the ITT population. A special mark-up will be done whether to tell if the treatment was performed before or/after surgery

Protocol:

Post-market clinical follow-up of a magnetic bone conduction implant

Protocol No:

CBAS5477

Version:

1.0

Page 14 of
18

4.10 Efficacy Analyses

4.10.1 Primary Efficacy Analysis

Primary efficacy analysis will be determined by analysis of change in free-field threshold audiometry:

PTA4 (mean of 500, 1000, 2000 and 4000Hz), from unaided versus Baha Attract System at the 6 months visit for the ITT population, using Fisher's two-sided non-parametric permutation test for paired observations at a significance level of 0.05.

4.10.2 Secondary Efficacy Analyses

Comparison regarding change from unaided hearing to Baha Attract System will be done according to the general methodology with Fisher's non-parametric permutation test for paired observations for the following variables:

- Threshold audiometry: PTA4 (Mean of 500, 1000, 2000 and 4000 Hz) at 4 weeks, 12 and 24 months
- Threshold audiometry: 250, 500, 1000, 2000, 3000, 4000 and 6000 Hz at 4 weeks, 6, 12 and 24 months
- Adaptive speech recognition in noise (50% performance) at 4 weeks, 6, 12 and 24 months
- Speech in quiet (50dB, 65dB and 80dB) at 4 weeks, 6, 12 and 24 months
- HUI3 at 6 and 24 months
- APHAB at 6 and 24 months
- SSQ at 6 and 24 months

Comparison of the Baha Attract System with the same sound processor worn on a Softband will be done according to the general methodology with Fisher's non-parametric permutation test for paired observations for the following variables:

- Threshold audiometry: PTA4 (Mean of 500, 1000, 2000 and 4000 Hz) at 4 weeks, 6, 12 and 24 months
- Threshold Audiometry: 250, 500, 1000, 2000, 3000, 4000 and 6000 Hz at 4 weeks, 6, 12 and 24 months
- Adaptive speech recognition in noise (50% performance) at 4 weeks, 6, 12 and 24 months
- Speech in quiet (50dB, 65dB and 80dB SPL) at 4 weeks, 6, 12 and 24 months

Magnetic force studied both total and by SP magnet. Changes in SP magnet strength will also be presented graphically in a flow graph.

All secondary efficacy analyses will be performed for both the ITT population and PP population. PTA4 will also be analyzed for the PP population in the same fashion as in the primary analysis.

Analyses of Threshold Audiometry, Adaptive speech recognition in noise and Speech in quiet, BC Direct, HUI, APHAB and The Speech, SSQ will be a made totally and also by SSD and Conductive/Mixed patients. This will be made only for the ITT populations.

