5.1 Rationale for the design of the clinical investigation

This investigation is designed to collect data regarding the usability and clinical performance of the Baha Attract System in subjects with hearing impairment that are candidates for Baha surgery.

The investigation will be performed in an open design since it is not possible to perform the investigation in a blinded fashion. The main evaluations of the investigation, i.e. free-field hearing tests, are relevant and objective methods.

This investigation is expected to demonstrate that the Baha Attract System performs within its intended use and is a suitable treatment for patients with a conductive or mixed hearing loss or single-sided sensorineural deafness.

While the Baha Attract System is approved for use in both adults and children, this investigation is limited to adult subjects. The paediatric population constitutes an inhomogeneous patient group (age-related), and currently there are no audiological tests that are suitable for comparisons across age ranges and across multiple countries/languages. Performance evaluation of the Baha Attract System in children should be performed as separate investigations.

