1.4 Sample Size

1.4.1 Sample size calculation for the primary efficacy analysis:

In order to achieve 90 % power to detect a clinically significant difference of 10 dB in free-field hearing thresholds between the unaided situation and the Baha Attract System at the 6 months visit with Fisher's non-parametric permutation test for paired observation, two-sided test with significance level 0.05, on the ITT population 20 evaluable subjects are needed assuming a within subject standard deviation (SD) of 13.0 dB. The within subject SD for change in PTA4 has been estimated to 12.3 dB in a previous study within Cochlear comparing unaided hearing with a BP100 sound processor on a Cochlear Baha Attract System, CBAS5477 42 (51) Softband versus unaided hearing. To compensate for a 10% drop out rate in the study 22 subjects should be included in the investigation.

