1.4.3 Overall sample size considerations

In order to achieve 90% power both for the primary analysis (PTA4, Baha Attract vs. unaided) and the secondary analysis of the primary variable (PTA4, Baha Attract vs. Softband), 46 evaluable subjects are needed. To compensate for a 10% drop out rate in the study 52 subjects will be included in the investigation.

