6 CHANGES OF ANALYSIS FROM PROTOCOL

No changes of the analyses according to the protocol are made.

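### SAP 4.10.2 adds within-type tests (SSD; conductive/mixed) with no exploratory label and no between-type comparison, so equal effects can look different by type, mainly against Softband or with an unbalanced split

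*SAP*

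**What the plan says.** SAP 4.10.2 states that the analyses of threshold audiometry, speech in noise, speech in quiet, BC Direct, HUI, APHAB and SSQ "will be a made totally and also by SSD and Conductive/Mixed patients. This will be made only for the ITT populations". The table list in SAP 7.1 carries this out. For each type it repeats the tables of Attract versus unaided and Attract versus Softband, and the questionnaire tables (Tables 14.2.7.1 to 14.2.18).

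SAP 4.1 sets the testing rule for everything: "All significance tests will be two-sided and performed at the 5% significance level". The only test it names for continuous variables is within-subject: "Fisher's non-parametric permutation test for paired observations will be used for all paired analyses of continuous variables". Neither document describes a two-group test, an interaction test, a multiplicity rule or an exploratory label for the by-type results.

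Protocol sections 8.1 to 8.5 list no analysis by type of hearing loss. SAP section 6 nevertheless says "No changes of the analyses according to the protocol are made".

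The sample size in SAP 1.4.3 is set "In order to achieve 90% power both for the primary analysis" and for the Softband comparison of PTA4, with 46 evaluable subjects in total and 52 enrolled. Neither document fixes how many subjects of each type are enrolled. Protocol 5.1 expects the study to show that the device "is a suitable treatment for patients with a conductive or mixed hearing loss or single-sided sensorineural deafness".

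**The concern.** The study enrols two clinically different groups and expects to support use in both, so type-specific results bear directly on its stated aim. If each type gets its own p-value at 5% and no estimate of the difference between types is planned, a natural reading is to set one p-value beside the other. A result that is significant in one type and not in the other does not show that the types differ. When one group is small it may reflect group size alone. At stake is a statement, in either direction, about whether the device works in SSD or in conductive/mixed loss that the data do not support.

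**Working it through.** **Inputs from the documents** (SAP 1.4 and 4.1; the same figures stand in Protocol 8.2)
- Two-sided alpha 0.05, paired test.
- Attract versus unaided: the plan aims to "detect a clinically significant difference of 10 dB in free-field hearing thresholds between the unaided situation and the Baha Attract System", "assuming a within subject standard deviation (SD) of 13.0 dB"; 20 evaluable subjects.
- Attract versus Softband: 1.5 dB, SD 3 dB; 46 evaluable subjects.

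**Assumptions, because the documents give no figure**
- Split of the 46 evaluable subjects between types: 23/23, 15/31 and 10/36.
- The same true effect and SD in both types, and independent results between types.
- A true unaided effect of 15 dB, and true Softband effects of 0.75 dB and 0 dB, as sensitivity cases.

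**Step 1: the plan's own figures.** Power of the paired t-test (the parametric counterpart of the permutation test) comes from the noncentral t distribution with n − 1 degrees of freedom and noncentrality (effect/SD) × √n.
- 10 dB, SD 13 dB, n = 20: 90.3%. The stated 20 is reproduced.
- 1.5 dB, SD 3 dB: 90% is reached at n = 44, and n = 46 gives 91.3%. The stated 46 is reproduced to within two subjects.

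**Step 2: by-type power and discordance.** With p1 and p2 the powers in the two types, the chance that exactly one type is significant is p1(1 − p2) + p2(1 − p1), and the chance that both are is p1 × p2. Worked example, Softband at 10/36: 0.293 × 0.169 + 0.831 × 0.707 = 0.637.

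| Comparison, true effect | Split | p1 | p2 | Exactly one | Both |
|---|---|---|---|---|---|
| Softband, 1.5 dB, SD 3 | 23/23 | 63% | 63% | 47% | 40% |
| | 15/31 | 44% | 77% | 53% | 34% |
| | 10/36 | 29% | 83% | 64% | 24% |
| Unaided, 10 dB, SD 13 | 23/23 | 94% | 94% | 11% | 89% |
| | 15/31 | 79% | 99% | 22% | 78% |
| | 10/36 | 58% | 99% | 42% | 58% |

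A simulated sign-flip permutation test gave the same discordance where it was run: 47% for Softband and 11% for unaided at 23/23.

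**Step 3: sensitivity to the true effect.**
- Softband at 0.75 dB: 33%, 34% and 35% at the three splits.
- Softband at no difference: 2 × 0.05 × 0.95 = 9.5% at every split.
- Unaided at 15 dB: 0.1%, 1.4% and 10%.

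**Step 4: what a direct comparison would give.** With equal SD, the 95% CI half-width for the between-type difference is t(0.975, 44) × SD × √(1/n1 + 1/n2), with t = 2.015.
- 23/23: 2.015 × 3 × 0.295 = 1.8 dB (Softband); 2.015 × 13 × 0.295 = 7.7 dB (unaided).
- 10/36: 2.015 × 3 × 0.357 = 2.2 dB; 2.015 × 13 × 0.357 = 9.4 dB.

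If the true effects are equal, such a comparison declares a difference 5% of the time.

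**The case against.** The strongest reply is that the large percentages come from Softband, while first priority goes to Attract versus unaided. There the plan needs only 20 evaluable subjects, so any split from 20/26 to 23/23 gives each type the power that the plan asked for overall. This stands, and it limits the point. Against unaided, discordance is modest at a balanced split and becomes large only when one type is small.

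The Softband figures also assume a true 1.5 dB, whereas Protocol 7.1 expects performance similar to the Softband or somewhat better. That stands too, and is why the smaller effects are shown.

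A reader might infer that p-values are the only way to read the by-type tables. SAP 4.1 does not support that: it already requires n, mean, SD and SEM for changes in continuous variables, so a reader could derive an interval or a between-type difference. What is missing is a planned one.

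A reader might also count the added tests. Repeating 126 ITT tests in two types gives 252, and 252 × 0.05 = 12.6 false positives if every null were true. The documents do not support that as a forecast, since the plan is powered for a 10 dB benefit over unaided hearing. The tests also overlap, because PTA4 averages four of the frequencies tested separately.

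Protocol 8.10 leaves detailed analyses to the SAP, and the by-type tables leave every protocol analysis intact, so the omission from SAP section 6 is minor. Neither document has an objective to compare the types, and a wide, non-significant difference could be misread as equality. The fix has to guard against that.

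**Conclusion.** The point holds as an inexpensive improvement to the secondary analyses. That the by-type analyses are significance tests is inferred from SAP 4.10.2 read with SAP 4.1 and the table titles. BC Direct is not among the listed tested comparisons and may be descriptive only.

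Under equal true effects, discordant by-type results are frequent for Softband at the plan's own 1.5 dB, whatever the split examined, and less frequent if the true difference is smaller. For the primary unaided comparison they are frequent only when the split is unbalanced, and they drop to about 10% or less if the true effect is 15 dB. A reader might infer that the plan as a whole would often show a false contrast between types; the plan's own unaided figures do not support this at a balanced split. All of these figures rest on assumed splits and on equal effect and SD in the two types. The pooled primary ITT test is not affected.

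**What to change.** In SAP 4.10.2:
- Label all by-type results exploratory, and report them as mean change with 95% CI.
- Add the between-type difference (SSD minus conductive/mixed) in 6-month PTA4 change, with 95% CI, for Attract versus unaided and for Attract versus Softband. These are two comparisons. Use a method that allows unequal variances, such as a Welch interval or a studentised permutation test, because the groups may differ in both size and spread.
- State that a non-significant between-type difference is not evidence of equal effect.

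In SAP section 6, record the by-type analyses as additions to the protocol.

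The cost is SAP wording and a small table from data already collected. The drawback is precision. With equal SD and splits from 23/23 to 10/36, the half-width is about 1.8 to 2.2 dB for Softband, wider than the 1.5 dB target, and 7.7 to 9.4 dB for unaided. By-type p-values would also no longer serve as stand-alone evidence for one type.
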